10.4 Participating Investigators and Roles (if applicable)

A list of the participating Investigators and their roles can be found in the Appendix B of this document and the Sponsor's Trial Master File.

10.5 Study Design

This is a monocentric, retrospective and consecutive series post-market clinical study. Consecutive series of cases implanted with the Zimmer Reconstruction System between 2010 and 2018 at the Hospital Azienda Ospedaliero Universitaria Senese in Siena, Italy will be identified and included in the study. The consecutive cases will be enrolled in the reverse chronological order that they were operated. This means enrollment will start with patients operated in 2018 and consecutively going backwards towards 2010 until the necessary number of cases has been reached.

10.6 EC Approval

Ethics Committee (EC) approval will be obtained prior to conducting this study. No informed consent, nor data protection regulation notice is needed as Zimmer Biomet will only receive a completely anonymized report and will not have access to any pseudonymized patient data.

10.7 Type and Timing of Observations

This study is designed to be retrospective. To avoid bias, consecutive series of cases will be identified and included in the study. The study duration is expected to be 12 months overall, which corresponds to time dedicated to the retrospective data collection from hospital charts from the pre-operative condition to the last consultation visit (at least 1-year post-operative), to conduct the analysis and to draft the final report.

10.8 Primary and Secondary Endpoint

The aim of this retrospective PMCF study is to collect data confirming safety, performance and clinical benefits of the Zimmer Reconstruction System and its instrumentation when used for temporary internal fixation and stabilization of fractures during the normal healing process.

10.8.1 Primary Endpoint

The primary endpoint is the radiographical and/or clinical assessment of fracture healing (performance).

10.8.2 Secondary Endpoint

The secondary endpoint is the assessment of safety by recording and analyzing the incidence and frequency of complications and adverse events. Relation of the events to implant, instrumentation and/or procedure should be specified. Subjects' outcomes will also be assessed.

10.9 Study Hypothesis

10.10 Since this study is an observational study no hypothesis is used in the study.

Financing of the Study

Funding for this clinical study is made available by Zimmer Biomet to support clinical data collection, EC review fees and other expenses associated with the conduct and execution of this study protocol as outlined in the fully executed Clinical Trial Agreement (CTA).

10.11 Definition of Completion of the Study

This study will be completed once an anonymized final report will be provided to and accepted by Zimmer Biomet on a total number of 83 cases treated with the Zimmer Reconstruction System.

11 Study Procedures

11.1 Study Participation

Each consecutive case implanted with the Zimmer Reconstruction System for temporary internal fixation and stabilization of fractures during the normal healing process between 2010 and 2018 at the Hospital Azienda Ospedaliero Universitaria Senese in Siena, Italy will be identified and included in the study until the required sample size of 83 cases is reached.

11.2 Informed Consent

All Subject related data will be kept anonymized. Patient confidentiality will be protected at all times and patients' identifiers will not be included in summaries of the data. The study sponsor will only receive an anonymized final report, therefore no patient consent is needed.

11.3 Information on Data Handling and Processing (GDPR notice)

Due to the retrospective design of this study and the delivery of anonymized data in a final report, no GDPR notice and consent is needed.

11.4 Study Logs

11.4.1 Subject Screening Log

All patients who received the Zimmer Reconstruction System between 2010 and 2018 must be entered into the Subject Screening Log sequentially regardless of their eligibility.

11.4.2 Subject Identification Log

The site shall maintain a log of all subjects included in the clinical investigation, assigning an identification code linked to their names, alternative subject identification or contact information. All patients who meet the inclusion criteria and none of the exclusion criteria must be entered on the log sequentially. If a subject receives multiple implants, a dataset will be recorded per fractured site. Each case, i.e. fractured site, will have a different identification code. A Subject Identification Log must be maintained throughout the study and is included in the Investigator Binder. This list is kept in a safe place in the hospital.

11.5 Determination of Eligibility and Enrollment

Patient eligibility for enrollment will be determined based upon the inclusion/exclusion criteria. Patients must have received the Zimmer Reconstruction System between 2010 and 2018 at the Hospital Azienda Ospedaliero Universitaria Senese in Siena, Italy and meet the inclusion criteria and none of the exclusion criteria in order to be included in the study.

11.6 Pre-operative Assessment

For each case, baseline data will be collected and will include, but will not be limited to the following:

- Inclusion/Exclusion Criteria
- Demographics:
 - Age at operation
 - Gender
 - Weight
 - Height
 - Concomitant diseases
 - Confounders for bone union
- Diagnosis:
 - Fracture cause (e.g. fall from height, motor vehicle accident)
 - Fracture classification (Tile's classification for pelvic ring fractures, AO or Judet classification for acetabulum fractures) (7; 8; 9; 10)
 - Open or closed fracture
 - Existence of additional fractures (i.e. polytrauma)
- Study deviation, if any

11.7 Surgical Techniques

The surgical technique for the Zimmer Reconstruction System is provided in the Regulatory Binder. The use of the study device was according to the IFU and the hospital's standard reconstruction procedures.

11.8 Surgical/Immediate Post-Operative Assessment

Operative and immediate post-operative data will include, but not be limited to the following:

- Op-Date
- Op-Duration (skin-to-skin, min)
- Product/Instrument specifications (e.g. catalogue number, plate type and size, screws used)
- Physical exam: ROM, motility, neurological basic exam
- Radiographic Evaluation
- Length of hospital stay
- Intra-op and immediate post-op complications, adverse events. (Relation of the events to implant, instrumentation and/or procedure should be specified)
- Study deviation, if any

11.9 Follow-up Procedures

Follow-up evaluation was conducted at a minimum of 1 year after surgery. Data collection will include but is not limited to the following:

- FUP date

- Fracture healing (union/non-union) evaluated by x-ray and/or clinically
- Pain and functional performance as reported by the Harris Hip Score (3)
- Adverse events and complications and date of its occurrence (relation to implant, instrumentation and/or procedure should be specified)
- Revisions/Implant removal date and reason (relation to implant, instrumentation and/or procedure should be specified)
- Study deviation, if any

11.10 Minimization of Loss to Follow-up

Due to the retrospective design of the study, no follow up visits are planned. Therefore no loss to follow-up is applicable.

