Standards	
The PMCF is compliant with the below:
 
 ISO 14155: 2020 - Clinical investigation of medical devices for human subjects - Good clinical practice [1]. The Declaration of Helsinki (DoH) - Ethical principles for medical research involving human subjects [2]. European Regulation (EU) 2017/745 [3]. MDCG 2020-10/1 Safety reporting in clinical investigations for medical devices under the

	Regulation (EU) 2017/74 [4]
Study Funding	Funding for this clinical study is made available by Zimmer Biomet to support clinical data collection, EC review fees and other expenses associated with the conduct and execution of this study protocol as outlined in the fully executed Clinical Trial Agreement.

5 Data Collection Overview

The following information and data will be collected on all cases:

Evaluation	Baseline			Last Consultation Visit (min. 1 year post-op)
	Prior to Surgery	Surgical/Operative	Immediate Post-Operative	
Inclusion/Exclusion Criteria	PI			
Demographic Evaluation	PI			
Physical Exam			PI	
Operative Information/ Surgical Device Information		PI		
Immediate Post-Operative Evaluation			PI	
Harris Hip Score [5].				PI
Fracture Healing (including x-rays and/or clinically)				PI
Protocol Deviation		If required		
Complications/Adverse Events (AE relation or not to device, instrumentation and/or procedure)				

PI: completed by Principal Investigator or qualified designee

6 Introduction and Purpose

Falls and motor vehicle accidents, the two most common mechanisms of traumatic injury [4, 5], sometimes result in fractures or other disruptions of the pelvic ring. Fractures following high-energy trauma are often associated with extensive soft tissue injuries. The state of the surrounding soft tissues and the local blood supply to the bone are the most important factors determining the tendency of the fracture to heal [6-12]. In high-energy pelvic trauma [fractures](#), temporary fixation with plates is indicated to stabilize the pelvic ring in order to control hemorrhage, creates high stability and reduces motion in the joint or at the fracture site.

The Zimmer Reconstruction System is a CE marked and FDA cleared implant system that has been in clinical use since 1995. The purpose of this retrospective PMCF study is to confirm safety, performance and clinical benefits of the Zimmer Reconstruction System when used for temporary internal fixation and stabilization of fractures during the normal healing process.

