12.4.5 Lost to Follow-up

Due to the retrospective design of this study, lost to follow-up are not applicable.

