16.1 Sample Size Calculation

The overall success rate of the Zimmer Reconstruction System will be calculated based on the percentage of subjects who have successful fracture healing. The following hypothesis will be tested by exact binomial test

$$\begin{aligned}H_0: E1 - E0 &\leq -\delta E \\H_a: E1 - E0 &> -\delta E\end{aligned}$$

Where:

$E0 = 90\%$, the expected success rate of similar devices to the Zimmer Reconstruction System [13]

$E1$ = the success rate in the Zimmer Reconstruction System treatment group

$\delta E = 0.10$, non-inferiority margin for fracture healing

In addition, one-sided 95% exact confidence Interval (CI), lower limit of the success rate, will be calculated.

The sample size was estimated based on the expected performance of 90% fracture union rate. The sample size includes a 10% non-inferiority margin ($90\% - 10\% = 80\%$). The expected Clinical Performance Rate of the Zimmer Reconstruction System is assumed as 90%.

Based on the hypothesis test above, a sample size of $n = 83$ will provide approximately 80% power for the one-sided exact binomial test at 0.05 significant level. The sample size was calculated using SAS for Windows version 9.4. The aim of this study is to include a total number of 83 cases treated between 2010 and 2018 with implants of the Zimmer Reconstruction System at the Azienda Ospedaliero Universitaria Senese in Siena, Italy.

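### Loss to follow-up is declared not applicable, yet healing is read at a visit at least 1 year after surgery that eligible cases need not have had, so the denominator of the primary test is undefined

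*Combined protocol and SAP*

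**What the plan says.** Section 11.10 notes that a retrospective study plans no visits and concludes: "Therefore no loss to follow-up is applicable". Section 12.4.5 says again: "Due to the retrospective design of this study, lost to follow-up are not applicable".

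The primary endpoint (10.8.1) is fracture healing, judged by x-ray, clinically, or both. In the Section 5 schedule it is collected only at the last consultation, at least one year post-operatively. Section 12.2.1 agrees, and 11.9 writes as if every case had such a visit: "Follow-up evaluation was conducted at a minimum of 1 year after surgery".

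Eligibility (8.1, 8.2, 11.5) depends on receipt of the device and the exclusion list, and sets no minimum follow-up. Enrolment starts in 2018 and works back towards 2010 (10.5). Each consecutive case is "included in the study until the required sample size of 83 cases is reached" (11.1).

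Section 16.1 defines success as the percentage of subjects whose fracture healed, tests it against 80% (90% less a 10-point margin), and states that 83 cases "will provide approximately 80% power for the one-sided exact binomial test at 0.05 significant level". Section 16.2 describes summaries only. No section defines an analysis set, a missing-outcome rule or a sensitivity analysis.

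**The concern.** That no visits are planned does not mean that every patient attended one. In a trauma series some eligible cases may have no record at one year or later because the patient died, was revised early, or did not come back. The plan does not say whether such a case counts as not healed, leaves the denominator, or gives way to an earlier case as enrolment moves backwards. These choices give different healing rates from the same charts.

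Section 10.7 relies on consecutive inclusion to avoid bias. If cases without a late visit were replaced, the series would become one of patients who returned, and that protection would be lost. If returning is related to healing, the rate, its lower confidence limit and the exact test are all affected. Revisions are reported as adverse events (12.4.2), but no section says how a revision before one year enters the healing endpoint.

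**Working it through.** **Inputs from Section 16.1:** null rate 0.90 − 0.10 = 0.80; assumed true rate 0.90; n = 83; one-sided exact binomial test at 0.05. The documents give no attendance, death or transfer figures, so every attendance rate and missing count below is an assumption.

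**1. The plan's own figure.** The critical value is the smallest r with P(X ≥ r | n = 83, p = 0.80) ≤ 0.05.
- r = 73, with exact size 4.1%.
- Power = P(X ≥ 73 | 83, 0.90) = 79.5%, which reproduces the stated value of about 80%.
- One-sided 95% exact lower limits: 80.4% at 73/83 and 79.0% at 72/83.
- The normal approximation ((1.645·√0.16 + 0.842·√0.09)/0.10)² = 82.9 also gives 83, so nothing was added for cases without an outcome.

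**2. If the 83 analysed cases all have a late visit because others were passed over.** Let s₁ and s₀ be the probabilities that a healed and an unhealed case has the visit. The apparent rate is q = p·s₁ / (p·s₁ + (1 − p)·s₀), and the chance of passing is P(X ≥ 73 | 83, q). For p = 0.80, s₁ = 0.90 and s₀ = 0.70, q = 0.72/(0.72 + 0.14) = 83.7%. With the two rates reversed, q = 0.56/(0.56 + 0.18) = 75.7%.

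| Healed / unhealed seen (assumed) | Apparent rate, true 80% | False-claim risk | Apparent rate, true 90% | Power |
|---|---|---|---|---|
| 90% / 90% | 80.0% | 4.1% | 90.0% | 79.5% |
| 90% / 70% | 83.7% | 18.7% | 92.0% | 93.6% |
| 90% / 60% | 85.7% | 34.7% | 93.1% | 97.3% |
| 90% / 50% | 87.8% | 56.7% | 94.2% | 99.1% |
| 80% / 90% | 78.0% | 1.6% | 88.9% | 68.5% |
| 70% / 90% | 75.7% | 0.4% | 87.5% | 53.3% |
| 60% / 90% | 72.7% | 0.07% | 85.7% | 34.7% |

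**3. If the 83 include cases without an outcome, and only evaluable cases are tested.** This is an alternative to step 2, and the two effects do not add. Exact power at a true 90% is 80.6% with 82 evaluable, 73.6% with 79, 77.4% with 76, 66.6% with 75 and 72.3% with 71. The sequence is saw-toothed because the test is discrete.

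**4. Tipping point.** Take 75/83 healed, the whole number nearest to 90% (0.90 × 83 = 74.7). Its lower limit is 83.3%. Adding unseen failures:
- one: 75/84, 82.0%
- two: 75/85, 80.9%
- three: 75/86, 79.7%, which no longer exceeds 80%

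If instead nine further consecutive cases were unseen (an assumed number), at least six must have healed: 80/92 gives 79.7% and 81/92 gives 81.0%.

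**The case against.** The strongest reply is that the plan never removes anyone. A late visit is not an eligibility criterion. Every implanted patient enters the screening log whether eligible or not (11.4.1), eligible patients are logged in sequence (11.4.2), and 11.1 speaks of each consecutive case. In context, 11.10 can be read as saying only that there are no prospective visits to protect. This stands in part: a reader might infer that such cases drop out silently, but the documents leave their handling undefined and do not direct removal or replacement. It does not supply the missing rule.

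A reader might also infer that the healing rate is biased upward. The documents do not support that as a fact. Patients with problems may keep attending while healed patients stop, and the lower rows of the table show the opposite effect.

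Nor would a failure at, say, four months disappear. Adverse events and revisions are collected with dates (11.9), summarised (12.2.1), and all revisions are reported as adverse events (12.4.2). What is missing is the link to the primary endpoint.

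Two points on size are also fair. The power loss is not a steady decline, and 75 evaluable cases sits at a low point of the saw-tooth. The nine-case tipping point is mild, since six of nine (67%) healing would be enough.

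**Conclusion.** The concern holds as a contradiction with an undefined denominator. Loss to follow-up is declared not applicable, while the primary endpoint depends on a visit that eligibility does not require. Eligible consecutive cases without that visit have no stated place in the healing rate, and the backward enrolment rule leaves room to replace them.

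The effect on the primary test may be material in either direction. Against a nominal 4.1%, the false-claim risk is 18.7% under the assumed 90%/70% attendance and 0.4% under 70%/90%, where power at a true 90% falls to 53%. Upward bias is plausible but unproven, and these figures rest entirely on assumed attendance. The tipping point needs no attendance assumption: for a result of 75/83, three unseen failures are enough to reverse the conclusion. The absence of a rule can be read directly from the text. It should be corrected before the charts are analysed.

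**What to change.** - Delete the not-applicable statements in 11.10 and 12.4.5.
- State that every eligible consecutive case counts, and that none is skipped or replaced for lack of a visit at one year or later.
- Have the sponsor state in advance how early revision for non-union or fixation failure, death, and union documented before one year enter the primary endpoint. The rule should be consistent with the one-year reading, and it is the sponsor's to choose.
- Report from the screening log and charts how many eligible cases lack a one-year assessment, and why.
- Give the exact test on evaluable cases together with the same test counting missing as not healed, and the tipping-point count.
- State in 16.1 that the power of about 80% refers to 83 evaluable cases.

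The cost is protocol wording and one extra table from records already being reviewed. The sensitivity result will be less favourable. If 83 are enrolled and 90% of evaluable cases heal, the chance of reaching 73 healed with missing counted as not healed is 31.3% with four missing and 1.6% with eight. That analysis is therefore a bound to report beside the main test and should not replace it.

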11.11 Radiographic Definitions and Methods

- Standard radiographs of the operated bone are captured during the last consultation visit, if available.
- Radiographic parameters include but are not limited to documentation of bone union and any significant radiographic findings.
- All radiographic evaluations performed according to the protocol will be reviewed by the investigator for significant radiographic findings. If a radiographic significant event is identified by the investigator he/she must document the event and report the radiographic findings as needed.

11.12 Recommended Revision Procedure

No revision arm is planned in this study.

11.13 Explant Procedure

In the event a study subject required a revision surgery all explanted components should have been returned to Zimmer Biomet for analysis. Upon removal, the investigator must record his/her findings i.e. damage on the device

In case of an explant procedure each component should be wrapped separately in a compress (or similar material) immersed in 10% formalin and place each component in a separate labeled container to prevent damage during shipping. The implant container(s) should be labelled to identify the catalog number, investigator name, case ID, date of removal, and include a statement indicating the implant is from a clinical study.

Each wrapped implant specimen and any tissue container should be placed into a Bio-hazardous Material bag. Bio-hazard bag should be placed inside a second sealed container.

All explanted devices should be returned to:

Zimmer Biomet

Attention: Product Services Department

[name]

[name]

USA

12 Reporting

12.1 Activities Required Prior to Initiation of the Study

12.1.1 Clinical Trial Agreement (CTA) and Financial Arrangements

A fully executed (signed by all required parties) CTA must be on file with the Sponsor prior to any investigator participating in this study. This agreement must explain the financial arrangement with the investigative site.

12.1.2 Ethics Committee Protocol Approval

This study protocol must be submitted to and approved by the Investigator's EC. A copy of the EC approval letter must be submitted to the Sponsor. The letter should identify the following:

- Protocol name and/or number.
- Date of EC meeting (if available).
- Date of approval.
- Date of expiration.
- Signature of EC.

12.1.3 Clinicaltrials.gov Registration

The Sponsor will be responsible for registering this study on www.ClinicalTrials.gov if required by local and national regulations.

12.2 Clinical Data Collection/Submission

12.2.1 Summary of Data Collection

Study data will be summarized in an anonymized final report. A final report template will be provided by the Sponsor. Study data will be collected from patients charts and transferred into a study-specific Excel database. The database will not be shared with the Sponsor. If a subject receives multiple implants, a dataset will be recorded per fractured site.

The following completion guidelines should be followed:

- Complete carefully and accurately.
- Be sure that data on the source documents match that which is entered in the database.
- Ensure that all fields are completed. The investigator must retain the subject data sources in accordance with local law and regulations.
- The investigator should take measures to prevent accidental or early destruction of the study related materials.

- Ensure that data in the final report is aligned with the source data.

The following information and data will be collected on all cases and summarized in the final report:

- **Preoperative Information:** Inclusion/Exclusion criteria, demographic data, and diagnosis.
- **Operative and Immediate Postoperative Information:** Date of surgery, duration of surgery, operated side, surgical device information (devices, ancillary devices, instrumentation), length of hospital stay, complications and adverse events.
- **Last Consultation Visit (at least 1 year post-op):** Date of visit, radiographic assessment of fracture healing (if available), clinical assessment of fracture healing, complications and adverse events and Harris Hip Score.
- **Adverse Events:** Complications, reoperations, revisions
- **Protocol Deviation,** if applicable

